Chronic fatigue, exercise intolerance and an inability to perform activities of daily living are hallmark symptoms of HF that negatively impact quality of life and prognosis.⁴ Physical disability is exacerbated by hospitalization, in which bed rest can cause acute muscle loss and further disability.^{5,6} The importance of hospital-acquired disability is underscored by the fact that reduced mobility at hospital discharge is predictive of 30 d readmissions.⁷ Even after acute HF symptoms resolve, many patients experience deficits in strength, balance and mobility and some never regain baseline function.⁶ Exercise training is beneficial in improving physical function in these patients, but classical exercise training is difficult during the acute post-phase discharge and cardiac rehabilitation is not covered for HFpEF patients.^{6,8} Many HF studies have focused on guideline directed medical therapy, however, few have focused on rehabilitation following hospitalization.⁸

A home based exercise intervention following hospital discharge may improve physical functional recovery, but there are numerous barriers to home exercise in HF patients. Neuromuscular electrical stimulation (NMES) offers a potential solution to these barriers, as it confers an exercise training effect without the physical requirements of traditional exercise. NMES is an inexpensive, safe, FDA- approved intervention which allows non-volitional initiation of muscle contractions that mimic resistance or aerobic type exercise, leading to training responses similar to traditional exercise.⁹ In older adults with chronic

disease, including HF patients, NMES improves muscle strength, but its ability to improve physical function is equivocal.¹⁰ Additionally, these studies were small and mostly performed in the outpatient setting with stable HFrEF patients without recent hospitalization.¹¹ Thus, whether NMES is effective in HFpEF and HFrEF patients at improving functional recovery following the acute disabling effects of hospitalization is unclear.⁹⁻¹¹

The purpose of this phase 4 randomized controlled trial is to establish the feasibility and efficacy of NMES administered to the quadriceps muscles to improve early functional recovery in older heart failure patients recently hospitalized for HF. Functional status will be objectively measured via the 6-minute walk test (6MW) and Short Physical Performance Battery tests (SPPB). Based on our pilot results in patients undergoing cardiac surgery, we hypothesize that the use of NMES will improve functional recovery.¹² Successful completion of this study will provide seminal data regarding the utility of NMES to improve functional capacity following hospitalization in heart failure patients, which may have implications for both readmission and long term prognosis

PURPOSE AND OBJECTIVES

Purpose: *The importance of the research and the potential knowledge to be gained should be explained in detail. Give background information.*

As the US population ages, there has been a rise in patients experiencing heart failure and, in turn, hospitalizations and readmissions.^{2,3} Focus has been placed on transitional care services for medical and surgical treatments, with little attention on physical rehabilitation services, despite the fact that patients prioritize this as an outcome of their treatment and that physical disability increases risk of complications and readmission.⁵⁻⁷ After hospitalization, HFpEF patients are severely deconditioned, but HFpEF is not a qualifying diagnosis for outpatient cardiac rehabilitation (CR). Our intervention aims to overcome this gap in rehabilitative care early after hospital discharge to improve functional recovery.

NMES is an innovative modality to bridge the critical gap in transition of care for these patients. Numerous trials have found that NMES improves muscle strength in stable HFrEF patients, but its effects on physical function are equivocal and only 1 small study examined NMES in clinically stable outpatient HFpEF patients.⁸⁻¹⁰ To our knowledge, the proposed study would be the first to investigate the utility of NMES to improve functional recovery in heart failure patients following hospitalization. Our rationale for targeting this period is based on our work in cardiac surgical patients, where functional gains during recovery after hospitalization were substantial, but also because regaining functional capacity during this period is important for long-term disability and clinical outcomes.^{11,12}

Results from this study can advance our existing treatment of heart failure in several ways. First, it will provide evidence of a novel rehabilitation intervention to improve functional status after a disabling event, such as hospitalization. With the exception of our own work, virtually no studies have examined NMES in the acute, post-discharge setting. Secondly, it may improve health outcomes given that hospital-acquired disability/deconditioning increases risk of complications and readmissions.^{11,12} Vermont's rural environment makes it challenging for patients to access medical care and rehabilitation. Our proposed study is conceptually innovative in developing a transitional rehabilitative intervention to address an important sector of older cardiac patients prone to hospital-acquired disability and rehospitalization. At this time, HFpEF patients are not eligible for CR and HFrEF patients must wait 6 weeks before CR enrollment, therefore, NMES can provide a portable, high value, home-based intervention to aid in the recovery of physical function for heart failure patients recently discharged from the hospital. Few studies have assessed the utility of NMES to improve functional recovery following an acute, disabling event.^{8-10,13} If successful, our data could advance a new model for early post-hospitalization rehabilitation.

References. *Include references to prior human or animal research and references that are relevant to the design and conduct of the study.*

References

Secondary Aim: Define the effects of NMES on self-reported physical function and quality of life at 4 weeks from baseline. We hypothesize that NMES will improve quality of life and self-reported physical function compared to the control.

METHODS AND PROCEDURES

Study Design: Describe the research design, including a description of any new methodology and its advantage over existing methodologies.

Study design: We will use a randomized-controlled trial design. Patients admitted for heart failure will be recruited and randomized to NMES or control for 4 weeks following hospital discharge. Patients will be stratified by sex and age. Baseline testing will occur prior to discharge and consist of functional assessment by 6MW and SPPB and completion of 2 questionnaires regarding quality of life and physical function (Kansas City Cardiomyopathy questionnaire {KCCQ} and (Medical Outcomes Study Short Form-36 {MOS SF-36}). After completion of the 4 week intervention period, patients will undergo Post-Testing which will be identical to Baseline testing.

Inclusion/Exclusion Criteria: Patients will be recruited if they: 1) have clinical diagnosis of heart failure being actively managed during hospitalization, 2) live within 30 miles of UVMMC and are between 50-90 years of age. Patients will be excluded if they have: 1) severe dementia/alzheimer's disease 2) an active malignancy, excluding non-melanoma skin cancer or low-grade prostate cancer under active surveillance; 3) exercise-limiting vascular or neuromuscular disease; 4) body mass index $\geq 40 \text{ kg/m}^2$ or 5*) an existing lower extremity blood clot or implantable cardioverter-defibrillator (ICD) or pacemaker (PPM).¹⁴ *The last criteria is a contraindication for NMES and we will withdraw patients if they develop a blood clot or receive an ICD or PPM.

Randomization and blinding: Patients will be randomized prior to hospital discharge to NMES or control using Pocock and Simon's covariate-adaptive randomization for which sex and age will be stratified. The unblinded project manager will train patients to use NMES device and oversee them during the intervention. The PI and co-I will be blinded to treatment assignment.

Interventions:

Usual care: Patients will not receive an NMES device. We opted not to use "sham" stimulation (eg, low-intensity stimulation below the threshold to initiate contraction) lessen the chance that patients may increase stimulation to produce contractions if there is perceived benefit. Patients will be contacted weekly to assess overall recovery. As there is currently no standard of care rehabilitation for these patients following discharge and NMES does not have demonstrated benefits, our study meets the requirements for clinical equipoise.

NMES: NMES will be carried out bilaterally on the quadriceps using a portable stimulator. Two adhesive electrodes will be placed to the anterior surface of each thigh. Symmetrical, biphasic pulses (400 μ s duration at 25 Hz) will be used, with a duty cycle of 25% (10 s on, 30 s off). Patients will be trained to conduct NMES sessions and will select stimulation intensities sufficient to cause visible muscle contractions below their pain threshold. Training in the use of the NMES device will begin prior to hospital discharge. After discharge, NMES sessions will occur 5 d/wk once per day for 45 min per occasion (5 min low-intensity warm-up, 40 min higher-intensity stimulation) for 4 wks. This program is meant to mimic an aerobic-type exercise stimulus and similar to prior protocols. Daily logs and weekly phone calls will be used to monitor compliance to maximize intervention fidelity with overall compliance measured using the device software.

Outcomes: The primary outcome is 6MW. Functional capacity measures and quality of life measures will be obtained at baseline (prior to hospital discharge) and at 4 weeks.

1. Baseline characteristics including age, body mass index, length of hospital stay, medications, and smoking status
2. Functional Capacity measures:
 - a. 6-MW test is a well-validated method to assess functional capacity in patients with cardiac disease and shows convergent validity with other indices of physical function. The test will be conducted under standardized conditions, as described by us.^{11,15} Distance walked (m) will be the primary outcome.
 - b. SPPB will be measured, as it is a widely used, easy to measure index of physical function in older adults. Thus, it provides context for the severity of disability in our population and the modifying effects of NMES for comparison to other studies.¹¹
3. Quality of Life measures:
 - a. Self-reported physical functioning assessment using the Medical Outcomes Study Short Form-36 (MOS SF-36) survey questionnaire (0-100 scale) with 100 representing excellent physical functioning¹⁶
 - b. Kansas City Cardiomyopathy questionnaire¹⁷
4. Hospital readmission and Emergency Department visits within 3 months
5. Activities of Daily Living measures:
 - a. Lawton Brody ADL questionnaire
 - b. Katz Index of Independence in Activities of Daily Living

Procedures: Describe all procedures (sequentially) to which human participants will be subjected. Identify all procedures that are considered experimental and/or procedures performed exclusively for research purposes. Describe the types, frequency and duration of tests, study visits, interviews, questionnaires, etc. Include required screening procedures performed before enrollment and while on study. Please provide in table, list or outline format for ease of review. (describe and attach all instruments)

Note: A clinical research protocol may involve interventions that are strictly experimental or it may involve some aspect of research (e.g., randomization among standard treatments for collection and analysis of routine clinical data for research purposes). It is important for this section to distinguish between interventions that are experimental and/or carried out for research purposes versus those procedures that are considered standard therapy. In addition, routine procedures performed solely for research purposes (e.g., additional diagnostic/follow-up tests) should be identified.

All of the procedures and interventions on volunteers recruited for these studies are carried out solely for research purposes, as none are part of standard therapy in heart failure patients.

Physiological Testing (Discharge and 1 month post discharge)

SPPB will be measured, as described by us (1), as this assessment is prognostic for functional competence and mortality in cardiac surgical patients (2). This measure takes ~5 min to perform and is comprised of: 5 repeated chair stands, balance testing (3 tasks each 10 s long) and a 4 meter walk. As increasing SPPB score in the first month post-discharge in a sample of elderly patients with diverse clinical backgrounds was associated with lower risk for rehospitalization and death (3), improvements in, or maintenance of, this metric would provide strong evidence for the clinical utility of NMES. We have experience with this measure in cardiac populations (4).

6 MW was developed to assess cardiopulmonary fitness in patients with lung and cardiac disease

(5), but has been used widely to assess disability in older adults (6) and is the most common metric used when seeking FDA approval for interventions to improve physical function. We have experience with this measure in heart failure patients (7).

Treatment phase

NMES will be carried out bilaterally on the quadriceps using a portable stimulator (EMPI Continuum). Two adhesive electrodes will be affixed to the anterior surface of each thigh: ~1 cm distal to the inguinal crease and ~5 cm proximal to the patella, just lateral to the midline of the thigh to assure that it does not interfere with incisions for vein harvest. Symmetrical, biphasic pulses (400 μ s duration at 25 Hz) will be used, with a duty cycle of 25% (10 s on, 30 s off). Patients will be trained to conduct NMES sessions and will select stimulation intensities sufficient to cause visible muscle contractions below their pain threshold. Training in the use of the NMES device will begin prior to day of discharge. . This training will consist of one session per day of ~15 min to familiarize the volunteer with the unit and the exercise/contraction stimulus. Upon discharge, NMES sessions will occur 5 d/wk once per day for 45 min per occasion (5 min low-intensity warm-up, 40 min higher-intensity stimulation) for 4 wks. This program is meant to mimic an aerobic-type exercise stimulus (8) and has been shown in heart failure patients to have functional benefits over a similar treatment period (9, 10). We acknowledge that the NMES training load is substantial, but have modeled this program on others that have shown morphological and functional effects in heart failure patients (11). At this exploratory stage, we feel that it is essential to use a stimulus that affects muscle size and function, with future studies modifying the NMES dose to establish a threshold that elicits a training effect with the highest subject compliance rate. Daily logs and weekly phone contacts will be used to track compliance, and compliance will be covertly monitored using the device software.

Control patients will not receive an NMES device. We chose not to utilize a control NMES intervention (eg, stimulation below threshold to elicit contraction) to mitigate the possibility that patients may increase stimulation to produce muscle contractions if there is perceived benefit. Rigorous control over the NMES stimulus is preferable to controlling for any effects of sub-threshold, cutaneous electrical stimulation. Patients will be contacted weekly to assess their recovery and discuss issues related to general health to equate the degree of interaction with study personnel to that of the NMES intervention group.

Quality of Life measures: will be assessed with the following questionnaires which will be obtained at baseline (discharge) and 1 month following discharge

- a. Self-reported physical functioning assessment using the Medical Outcomes Study Short Form-36 (MOS SF-36) survey questionnaire (0-100 scale) with 100 representing excellent physical functioning
- b. Kansas City Cardiomyopathy questionnaire

Activities of Daily Living measures:

- a. Lawton Brody ADL questionnaire
- b. Katz Index of Independence in Activities of Daily Living

References cited above:

1. Ades, P. A., Savage, P. D., Cress, M. E., Brochu, M., Lee, N. M., and Poehlman, E. T. (2003) Resistance training on physical performance in disabled older female cardiac patients. *Med Sci Sports Exerc* **35**, 1265-1270
4. Rengo, J. L., Savage, P. D., and Ades, P. A. (in press) Directly measured physical function in cardiac rehabilitation. *J Cardiopulm Rehabil Prev*
5. Guyatt, G. H., Sullivan, M. J., Thompson, P. J., Fallen, E. L., Pugsley, S. O., Taylor, D. W., and Berman, L. B. (1985) The 6-minute walk: a new measure of exercise capacity in patients with chronic heart failure. *Can Med Assoc J* **132**, 919-923

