Statistical Considerations: *Delineate the precise outcomes to be measured and analyzed. Describe how these results will be measured and statistically analyzed. Delineate methods used to estimate the required number of subjects. Describe power calculations if the study involves comparisons. Perform this analysis on each of the primary and secondary objectives, if possible.*

Statistical Analysis:

Primary outcome is the 6MW. Other outcomes include SPPB, KCCQ and MOS SF-36 questionnaire results and subsequent ER visits and hospitalizations. The two experimental groups will be compared on baseline demographic characteristics using one-way Analysis of Variance (ANOVA) for continuous measures and chi-square tests (or Fisher's Exact Test) for categorical variables. Our primary outcome is to assess changes in physical function (specifically 6MW) between study groups to test whether NMES improves functional recovery from discharge to 4 weeks. We will use analysis of covariance to model primary and secondary outcomes, as this is the preferred model to assess data in pre-post RCTs. In this model, the 4-week post-discharge value is the dependent variable and the value at hospital discharge is a covariate. Sex interactions for response to NMES will be examined. We will assess QOL by questionnaires to determine if NMES improves patient-reported QOL vs. usual care. Clinical and other factors that may modify the response to NMES (eg, length of stay, etc) can be included in the model to control for potential confounders that might differ by group in the event that randomization fails to equate groups.

Sample Size Calculation:

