Risks/Benefits: Describe any potential or known risks. This includes physical, psychological, social, legal or other risks. Estimate the probability that given risk may occur, its severity and potential reversibility. If the study involves a placebo or washout period, the risks related to these must be addressed in both the protocol and consent. Describe the planned procedures for protecting against or minimizing potential risks and assess their likely effectiveness. Where appropriate, discuss plans for ensuring necessary medical or professional intervention in the event of adverse effects to the subjects. Discuss the potential benefits of the research to the subjects and others. Discuss why the risks to the subjects are reasonable in relation to the anticipated benefits to subjects and others. Discuss the importance of the knowledge gained or to be gained as a result of the proposed research and why the risks are reasonable in relation to the knowledge that reasonably may result. If there are no benefits state so.

Potential risks: Below we have highlighted those procedures/measurements that have anything greater than negligible risk to the volunteers' health for each phase of the study.

Testing: Risks associated with functional testing are minimal. All of the activities are similar to those performed during the conduct of normal daily activities. If volunteers are unable to do any of the activities because of limitations of their heart condition, they will not be required to perform them and testing will be monitored by trained personnel.

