The PIs or the study coordinator ([name]) will monitor the safety of the research procedures/interventions for this study. [name] or [name] will be available on-site for all assessments that may pose safety concerns for volunteers. Additionally, subjects will be contacted weekly to review device use and any difficulty or issues that may have occurred since the last contact. General muscle soreness is expected in some subjects and will not be considered an adverse event. Subjects reporting severe muscle discomfort limiting daily activity or other potential adverse events (i.e. skin irritation) will be instructed to discontinue device use pending further review. In this context, study personnel will be readily available to monitor volunteer safety throughout the study. If an event occurs that affects participant safety, [name] will alert [name], who will adjudicate the event with respect to its severity, expectedness and relatedness to participation in the study. Because numerous studies in our laboratories and others have demonstrated the safety of this regimen of testing in patients from with a broad range of clinical backgrounds (eg, heart failure patients, cancer patients, advanced-stage, knee OA patients; healthy elderly), we expect minimal problems related to testing or the intervention. Considering the low risk nature of these studies, we have not incorporated "stoppage criteria" for the overall study. Instead, [name] will decide whether an individual participant should continue with the study following occurrence of any adverse events or unanticipated problems, taking into consideration what is in the best interest of each individual patient.

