Volunteers will be withdrawn if the research team, clinician and/or safety officer feels that further participation in the study or performance of any procedure associated with this study would, in any way, put the volunteer at undue risk or not be in their best interest. Moreover, volunteers may be withdrawn if s/he fails to attend scheduled visits or do not comply with instructions from research staff.

Sources of Materials: Identify sources of research material obtained from individually identifiable human subjects in the form of specimens, records or data. Indicate whether the material or data will be obtained specifically for research purposes or whether use will be made of existing specimens, records or data.

An individual research record will be kept on each volunteer in compliance with HIPAA standards. This record will contain identifying data, demographic information and results from all clinical research measurements and evaluations. The results of all testing will be kept confidential. All materials gathered in conjunction with the proposed studies will be used for research purposes only and will be available only to research personnel working on these studies, who have obtained proper training in human subjects research and privacy protection.

DRUG AND DEVICE INFORMATION

Investigators are encouraged to consult the UVM Medical Center Investigational Pharmacy Drug Service ([name]) prior to finalizing study drug/substance procedures.

Drug (s)

Not applicable

Drug name – generic followed by brand name and common abbreviations. Availability – Source and pharmacology; vial or product sizes and supplier. If a placebo will be used, identify its contents and source. (attach investigational drug brochure)

Preparation: Reconstitution instructions; preparation of a sterile product, compounded dosage form; mixing guidelines, including fluid and volume required. Identify who will prepare.

Storage and stability – for both intact and mixed products.

Administration – Describe acceptable routes and methods of administration and any associated risks of administration.

Toxicity – Accurate but concise listings of major toxicities. Rare toxicities, which may be severe, should be included by indicated incidence. Also adverse interactions with other drugs used in the protocol regimen as well as specific foods should be noted. Address significant drug or drug/food interactions in the consent form as well. List all with above details.

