
Vulnerable Populations: *Explain the rationale for involvement of special classes of subjects, if any. Discuss what procedures or practices will be used in the protocol to minimize their susceptibility to undue influences and unnecessary risk (physical, psychological, etc.).*

Not applicable

Number of Subjects: *What is the anticipated number of subjects to be enrolled at UVM/UVM Medical Center and in the case of a multi-center study, with UVM/UVM Medical Center as the lead, the total number of subjects for the entire study.*

The proposed sample of 60 participants is based on having sufficient power to calculate differences in our primary outcome (6MW) between the control condition and the intervention and accommodating for potential drop outs (20%) from the study. We will need to recruit 60 patients with our target of 48 patients to complete the study

Inclusion/Exclusion Criteria: Eligibility and ineligibility criteria should be specific. Describe how eligibility will be determined and by whom. Changes to the eligibility criteria at a later phase of the research have the potential to invalidate the research.

Inclusion/Exclusion Criteria: Patients will be recruited if they: 1) have clinical diagnosis of heart failure being actively managed during hospitalization, 2) live within 30 miles of UVMMC and are between 50-90 years of age. Patients will be excluded if they have: 1) severe dementia/alzheimer's disease 2) an active malignancy, excluding non-melanoma skin cancer or low-grade prostate cancer under active surveillance; 3) exercise-limiting vascular or neuromuscular disease; 4) body mass index ≥ 40 kg/m² or 5*) an existing or history of deep vein thrombosis (DVT) or have an implantable cardioverter-defibrillator (ICD) or pacemaker (PPM).¹ *The last criteria is a contraindication for NMES and we will withdraw patients if they have an existing or history of deep vein thrombosis of the lower extremities or have an ICD or PPM

Literature cited:

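### A clot, ICD or pacemaker after randomisation triggers withdrawal only because NMES is contraindicated; that supports stopping the device in the NMES arm, not ending follow-up in either arm.

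*Combined protocol and SAP*

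**What the plan says.** The rule appears twice. In Methods and Procedures, Inclusion/Exclusion Criteria, the footnote to criterion 5 reads: "The last criteria is a contraindication for NMES and we will withdraw patients if they develop a blood clot or receive an ICD or PPM". In the later Inclusion/Exclusion Criteria section, under Subject Characteristics, the corresponding footnote says "we will withdraw patients if they have an existing or history of deep vein thrombosis of the lower extremities or have an ICD or PPM". Neither names an arm, and neither says whether withdrawal means stopping the stimulator or leaving the study.

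Other sections bear on how to read it:

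- **Procedures, Treatment phase:** "Control patients will not receive an NMES device".
- **Withdrawal Procedures:** "Volunteers will be withdrawn if the research team, clinician and/or safety officer feels that further participation in the study" would put them at undue risk or not serve their interest. Here withdrawal means leaving the study, and no later follow-up is described.
- **Adverse Event and UAP Reporting:** severe muscle discomfort and other potential adverse events lead to a pause in device use pending review. After any adverse event a named investigator "will decide whether an individual participant should continue with the study following occurrence of any adverse events or unanticipated problems". Clots and cardiac devices are not mentioned.
- **Statistical Analysis:** in the ANCOVA, "the 4-week post-discharge value is the dependent variable and the value at hospital discharge is a covariate". No analysis set and no method for missing 4-week values is given.
- **Outcomes:** the list includes "Hospital readmission and Emergency Department visits within 3 months".

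**The concern.** The footnote's only justification is that NMES is contraindicated after the event. That is a sound reason to take a patient off the stimulator. It is not a reason to cancel the 4-week walk test or questionnaires, and in a control patient there is no stimulator to stop.

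A new clot or a newly implanted cardiac device in the month after a heart failure admission is related to prognosis. Removing such patients after randomisation selects the analysed sample on something that happened during the trial. Treatment may also influence one of the triggers: under Risks/Benefits the protocol notes a suggestion that NMES raises DVT risk, alongside published reports that it lowers it. The rule could therefore end follow-up after the very safety event that the protocol singles out.

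At stake are the 4-week 6-minute walk, SPPB and questionnaire data of these patients. Whether the 3-month readmission and emergency visit outcome would still be collected for them is left unclear.

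**Working it through.** **1. What the text supports.** The rule says patients, without an arm, and Withdrawal Procedures uses the term for leaving the study, so the plain reading is that both arms are covered and follow-up ends. An NMES-only reading is possible because only that arm has a contraindicated treatment. No section settles the question or keeps these patients in follow-up.

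**2. The plan's own sample size.** Inputs from Sample Size Calculation: difference 50 m, SD 60 m, alpha 0.05 (taken as two-sided), power 80%, dropout 20%. The two-sample t-test needs 23.6, so 24 per arm; power at 24 is 80.7%. Recruitment is 48/0.8 = 60, or 30 per arm, which leaves 30 − 24 = 6 per arm for dropout. The plan's figures reproduce.

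**3. Patients lost.** The documents give no rate for these events, so the rate p by week 4 is assumed. Expected withdrawals per arm are 30p. The last three columns apply only if these losses fall wholly on top of the 6, leaving n = 24 − 30p. ANCOVA uses residual SD = 60·√(1 − r²) and 2n − 3 degrees of freedom; the plan states no correlation r, so two values are shown.

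| p | 30p | Share of the 6 | n if on top | t-test power | ANCOVA, r = 0.3 | ANCOVA, r = 0.5 |
|---|---|---|---|---|---|---|
| 2% | 0.6 | 10% | 23.4 | 79.6% | 83.2% | 89.6% |
| 5% | 1.5 | 25% | 22.5 | 78.0% | 81.7% | 88.4% |
| 10% | 3.0 | 50% | 21 | 75.0% | 78.8% | 86.0% |

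If the losses fall inside the allowance, n stays at 24 and planned power does not change.

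**4. Bias.** Suppose a fraction p of an arm would walk g metres less than the rest, whose mean is m (for ANCOVA, g is the gap after baseline adjustment). The full-arm mean is (1 − p)m + p(m − g) = m − pg. Removing the affected patients leaves m, a rise of pg. The gap is also assumed: 60 m is one SD in the plan, 100 m is a high case and 30 m a low case.

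*Both arms withdrawn:* shift = (p_NMES − p_control)·g, with the same g in each arm. The sign follows whichever arm has more events.

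| Rates in the two arms | g = 30 m | g = 60 m | g = 100 m |
|---|---|---|---|
| equal | 0 | 0 | 0 |
| 5% vs 2% | 0.9 m | 1.8 m | 3.0 m |
| 10% vs 5% | 1.5 m | 3.0 m | 5.0 m |

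*NMES arm only, equal rates:* shift = pg in favour of NMES, because affected controls stay in.

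| p | g = 30 m | g = 60 m | g = 100 m |
|---|---|---|---|
| 2% | 0.6 m | 1.2 m | 2.0 m |
| 5% | 1.5 m | 3.0 m | 5.0 m |
| 10% | 3.0 m | 6.0 m | 10.0 m |

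**5. Patients who could not walk anyway.** Under Risks/Benefits, Testing, if the heart condition prevents an activity, "they will not be required to perform them and testing will be monitored by trained personnel". If only a share s of affected patients could do the walk test, the shift due to the rule is about s·p·g; at s = 0.5 every entry in the bias tables halves. The same share limits what the fix can recover.

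**The case against.** The strongest reply is about weight. On the plain reading the rule treats both arms alike and does nothing to the comparison when event rates and outcome gaps are equal. The 6 to 10 m shifts need the less natural NMES-only reading, a 10% event rate within four weeks that nothing in the documents supports, and a gap of at least one SD. The 20% allowance does not exclude these withdrawals, so the power cost may be nil. All of this stands.

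It can also be said that the ANCOVA's lack of a missing-data method affects every dropout and is a wider gap. That is right, but this rule creates missing values by instruction, and that part can be avoided. A new clot might be handled through the device pause in the adverse event section; however, that section does not name clots or cardiac devices, while the footnote prescribes withdrawal.

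Three stronger readings are tempting and not supported:

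- A reader might infer that the 3-month readmission outcome is lost for these patients. The plan is silent on this.
- A reader might infer that the second footnote concerns enrolment status only. Its wording on an existing DVT or having a cardiac device also catches on-study events; only a past DVT is purely a baseline characteristic.
- A reader might count the coagulopathy exclusion, under Risks/Benefits and in the device risk assessment, as a conflicting clot definition. It is a separate exclusion.

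The two eligibility lists do differ on DVT (existing, versus existing or past), but that is a separate minor inconsistency and adds no weight here.

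**Conclusion.** The concern holds in a limited form. Followed as written, the footnote removes randomised patients from the 4-week analysis for a reason that supports stopping the stimulator in one arm only. The trial is right to stop NMES after these events; ending follow-up is the avoidable part.

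The effect is probably small and cannot be sized from the documents. With both arms covered it is zero at equal rates and equal gaps, and 0.9 to 5.0 m in the unequal-rate cases shown. With the NMES arm only it is 0.6 to 5.0 m at rates of 2% to 5%, and 3.0 to 10.0 m at 10%. For scale, the plan's design difference is 50 m and its minimal important difference 25 m. Every event rate and gap behind these figures is assumed. A reader might infer that the rule undermines the primary result or leaves the trial underpowered; the documents do not support that. The change is worth making because the exclusion is unnecessary and cheap to remove.

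**What to change.** In both Inclusion/Exclusion Criteria sections, replace the withdrawal clause with:

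*NMES patients who develop a clot or receive an ICD or PPM permanently stop the device. No patient in either arm is withdrawn from the study for this reason alone. All remain in follow-up for the 4-week assessments (tests their clinician permits, questionnaires otherwise) and the 3-month readmission and emergency visit outcome, and are analysed in the arm to which they were randomised.*

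In the Subject Characteristics version, keep a past DVT as an enrolment exclusion only, not a ground for withdrawal.

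The cost is wording. These assessments are already planned for everyone, so no visits, staff or patients are added. The adverse event section and Withdrawal Procedures still allow any individual at undue risk to be taken out. The limitation is that some affected patients may be unable to do the walk test, so recovery of primary outcome data would be partial. How to handle those remaining missing values belongs in the Statistical Analysis section and is not solved by this change.
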